3.3. Secondary Objectives

3.3.1. Evaluate retention-in-care in patients receiving CAB-LA vs oral PrEP

3.3.2. Evaluate PROs (including PrEP Medication Satisfaction, PrEP Acceptance, PrEP-Related Stigma, and reasons for PrEP discontinuation) in patients receiving CAB-LA vs oral PrEP

3.3.3. Evaluate the acceptability, appropriateness, and helpfulness of a digital health companion program for PrEP

[figure not shown]

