6.14.1.3. Patient-reported Outcomes

Patient-reported outcomes will be assessed through surveys. Medication satisfaction will be measured by the HIV Treatment Satisfaction Questionnaire (HIVSTQ) adapted for PrEP and PrEP stigma will be measured by the PrEP Stigma Scale at months 1, 5, and 11. PrEP acceptance will be measured by the Modified Injection Treatment Acceptance Questionnaire (Modified I-TAQ) at months 3, 9, and 12. Barriers to adherence to oral PrEP and reasons for PrEP discontinuation will be assessed through brief behavioral surveys every month after the initiation of PrEP. Barriers to adherence to CAB-LA injections and reasons for PrEP discontinuation will be assessed through brief behavioral surveys at months 1, 3, 5, 7, 9, and 11.

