You are treated with less respect than other people are. 
  Never  Less than once a year  A few times a year  A few times a month  At least once a week  Almost every day 	15
People act as if they're better than you. 
  Never  Less than once a year  A few times a year  A few times a month  At least once a week  Almost every day 	16
What do you think is the main reason for these experiences? (Select 1) 
  Your gender  Your sexual orientation  Your race  Your religion  Some aspect of your physical appearance  Your education or income level  Other: [Write in] 	17

End Message: Thank you for completing this survey!

Persistence Assessment

Activity Title: Are You Still Taking PrEP?

Activity Description: In this short survey, we'll ask you some questions about your PrEP journey and any challenges you may have encountered.

Activity:

1. Are you still getting PrEP medicine by an injection from your healthcare provider?

- Yes, I am taking PrEP ([branching logic to question 4](#))
- No, I stopped taking PrEP ([branching logic to question 2](#))

2. If you stopped taking PrEP, which of the following best describes the reason(s) why?

[Select up to 2]

- I no longer feel I needed to take PrEP ([branching logic to question 3 if selected](#))
- It was too difficult to take to take PrEP as prescribed with my lifestyle
- I felt I was being judged by others for taking PrEP
- I experienced side effects from taking PrEP

- I take too many medications
- There were too many appointments as part of my PrEP care
- I tested positive for HIV
- Other: [Fill in the blank]

3. Which of the following best describes why you no longer feel you need to take PrEP?

- I am no longer having sex
- I am in a monogamous relationship
- I am no longer using injectable drugs
- My partners and I are all regularly using condoms and getting tested for HIV
- Other: [Fill in the blank]

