4. If you are still taking PrEP, what challenges have you experienced?

- Have not experienced any challenges
- Keeping up with clinical visits and laboratory testing
- Concerns about side effects
- Finding transportation to my appointments
- Stigma or discrimination from family, friends, or partner(s)
- Stigma or discrimination from healthcare professionals
- Other: [Fill in the blank]

5. Did a healthcare provider (for example, a doctor, nurse or pharmacist) or navigator ever ask you what may make it difficult for you to take PrEP? (Month 1 & 11)

- Yes
- No
- Unsure

Activity Type: Patient Reported Outcomes – Set 1

Activity Title: Your Experiences With PrEP

Activity Description: This month we'll ask you to answer questions about your experience using PrEP and your thoughts about PrEP-related stigma. We'll also ask some questions about your experience using this mobile app to support you taking PrEP. The survey is 3 parts with a total of 24 questions. It should take you 10-15 minutes to complete.

Activity:

Part 1. Tell us about your experience using PrEP

The following questions are related to the PrEP medicine you use to protect you from HIV infection and your experience over the **past 4 weeks**. Please answer each question by selecting a number on each of the scales.

1. How satisfied are you with your **current medicine** for PrEP?
 - Very satisfied
 - Satisfied

- Neither satisfied or dissatisfied
 - Dissatisfied
 - Very dissatisfied
2. How **bothered** are you by **any side effects** from the medicine you use for PrEP?
- Very unbothered
 - Unbothered
 - Neither unbothered or bothered
 - Bothered
 - Very bothered
 - I have not experienced any side effects in the last 4 weeks
3. How satisfied are you with the **convenience** of PrEP recently?
- Very satisfied
 - Satisfied
 - Neither satisfied or dissatisfied
 - Dissatisfied
 - Very dissatisfied
4. How satisfied are you with the **discreetness** of PrEP recently?
- Very satisfied
 - Satisfied
 - Neither satisfied or dissatisfied
 - Dissatisfied
 - Very dissatisfied
5. How satisfied are you with your **understanding of using PrEP** to prevent HIV?
- Very satisfied
 - Satisfied
 - Neither satisfied or dissatisfied
 - Dissatisfied
 - Very dissatisfied
6. How satisfied are you with the extent to which PrEP **fits in with your lifestyle**?
- Very satisfied
 - Satisfied
 - Neither satisfied or dissatisfied
 - Dissatisfied
 - Very dissatisfied

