You are treated with less respect than other people are. 
  Never  Less than once a year  A few times a year  A few times a month  At least once a week  Almost every day 	15
People act as if they're better than you. 
  Never  Less than once a year  A few times a year  A few times a month  At least once a week  Almost every day 	16
What do you think is the main reason for these experiences? (Select 1) 
  Your gender  Your sexual orientation  Your race  Your religion  Some aspect of your physical appearance  Your education or income level  Other: [Write in] 	17

End Message: Thank you for completing this survey!

Persistence Assessment

Activity Title: Are You Still Taking PrEP?

Activity Description: In this short survey, we'll ask you some questions about your PrEP journey and any challenges you may have encountered.

Activity:

1. Are you still taking PrEP medicine by mouth?

- Yes, I am taking PrEP (branching logic to question 4)
- No, I stopped taking PrEP (branching logic to questions 2)

2. Over the past week, how many days did you miss taking PrEP?

- 0
- 1
- 2
- 3
- 4
- 5
- 6

7

3. If you stopped taking PrEP, which of the following best describes the reason(s) why? [Select up to 2]

- I no longer feel I needed to take PrEP (branching logic to question 3 if selected)
- It was too difficult to take PrEP with my schedule
- I did not want people to know I was taking it or I felt I was being judged by others for taking PrEP
- I did not like the side effects
- I take too many medications
- There were too many appointments as part of my PrEP care
- I tested positive for HIV
- Other: [Fill in the blank]

4. Which of the following best describes why you no longer feel you need to take PrEP?

- I am no longer having sex
- I am in a monogamous relationship
- I am no longer using injectable drugs
- My partners and I are all regularly using condoms and getting tested for HIV
- Other: [Fill in the blank]

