5. If you are still taking PrEP, what challenges have you experienced? [Select up to 2]

- Have not experienced any challenges
- Remembering to take PrEP every day
- Keeping up with clinical visits and laboratory testing
- Concerns about side effects
- Finding transportation to my appointments
- Stigma or discrimination from family, friends, or partner(s)
- Stigma or discrimination from healthcare professionals
- Other: [Fill in the blank]

6. Did a healthcare provider (for example, a doctor, nurse, or pharmacist) or navigator ever ask you what may make it difficult for you to take PrEP?

- Yes
- No
- Unsure

End Message: Thank you for completing this survey!

Patient Reported Outcomes – Set 1

Activity Title: Your Experiences with PrEP

Activity Description: This month we'll ask you to answer questions about your experience using PrEP and your thoughts about PrEP-related stigma. We'll also ask some questions about your experience using this mobile app to support you taking PrEP. The survey is 3 parts with a total of 24 questions. It should take you 10-15 minutes to complete.

Activity:

Part 1. Tell us about your experience using PrEP

The following questions are related to the PrEP medicine you use to protect you from HIV infection and your experience over the **past 4 weeks**. Please answer each question by selecting a number on each of the scales.

1. How satisfied are you with your **current medicine** for PrEP?
 - Very satisfied
 - Satisfied
 - Neither satisfied or dissatisfied
 - Dissatisfied
 - Very dissatisfied
2. How **bothered** are you by any **side effects** from the medicine you use for PrEP?
 - Very unbothered
 - Unbothered
 - Neither unbothered or bothered
 - Bothered
 - Very bothered
 - I have not experienced any side effects in the last 4 weeks
3. How satisfied are you with the **convenience** of PrEP recently?
 - Very satisfied
 - Satisfied
 - Neither satisfied or dissatisfied
 - Dissatisfied
 - Very dissatisfied
4. How satisfied are you with the **discreetness** of PrEP recently?
 - Very satisfied
 - Satisfied
 - Neither satisfied or dissatisfied
 - Dissatisfied
 - Very dissatisfied
5. How satisfied are you with your **understanding of using PrEP** to prevent HIV?
 - Very satisfied
 - Satisfied

- Neither satisfied or dissatisfied
- Dissatisfied
- Very dissatisfied
6. How satisfied are you with the extent to which PrEP **fits in with your lifestyle?**
- Very satisfied
- Satisfied
- Neither satisfied or dissatisfied
- Dissatisfied

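### The two Persistence Assessment forms differ where route does not require it, so the secondary CAB-LA versus oral comparison of stopping reasons and challenges is not like with like

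*Combined protocol and SAP*

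**What the plan says.** Section 3.3.2 lists stopping reasons among the outcomes to be evaluated: "and reasons for PrEP discontinuation) in patients receiving CAB-LA vs oral PrEP". Section 6.14.1.3 and the Study Outcomes Table put barriers to adherence in the same secondary endpoint. For oral PrEP, barriers and "reasons for PrEP discontinuation will be assessed through brief behavioral surveys every month after the initiation of PrEP"; for CAB-LA the surveys fall in months 1, 3, 5, 7, 9 and 11. Section 6.2 gives the same two schedules for the persistence assessments.

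The data come from two forms, in Appendix B (CAB-LA) and Appendix C (oral). Each has a stopping-reason item of eight options, limited to two choices in both arms. Three options differ:

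- Stigma: "I felt I was being judged by others for taking PrEP" for CAB-LA; "I did not want people to know I was taking it or I felt I was being judged by others for taking PrEP" for oral.
- Side effects: "I experienced side effects from taking PrEP" for CAB-LA; "I did not like the side effects" for oral.
- Difficulty: the CAB-LA option refers to following the prescription given one's lifestyle; the oral option refers to one's schedule.

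People still on PrEP get a challenges item. The oral stem carries a limit: "If you are still taking PrEP, what challenges have you experienced? [Select up to 2". The CAB-LA stem, "If you are still taking PrEP, what challenges have you experienced", carries none. The oral list also has one extra option, about remembering a daily dose.

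Section 7 gives no test, option mapping or rule for repeated answers for these items.

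**The concern.** When arms are compared on a fixed-choice item, the choices should be the same unless the route of administration forces a difference. A daily-pill option is properly specific to the oral arm. Privacy, judgement, side effects and difficulty are not. The CAB-LA instruments themselves treat concealment as relevant to injections: Set 1 of the patient-reported outcomes asks whether injection appointments should be kept hidden, and Set 2 asks whether the participant felt a need to hide attendance.

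At stake is whether a difference in why people stop, or in what they find hard, reflects the product or the questionnaire. The broader oral stigma option would tend to make privacy and stigma look like a problem of pills. For challenges, two features pull in opposite directions: the cap lowers oral counts at each survey, and the greater number of surveys raises oral counts accumulated over the year.

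**Working it through.** The plan gives no rate or precision figure for these items, so there is no plan figure to reproduce. All rates below are assumptions.

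**Stopping reasons: the joined option.** Suppose 10% of stoppers in each arm felt judged, and a further share q stopped only for privacy. The oral option records 10% + q. The CAB-LA option records 10%, if privacy answers go to the write-in.

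| q | Oral stigma option | CAB-LA stigma option |
|---|---|---|
| 5% | 15% | 10% |
| 10% | 20% | 10% |
| 20% | 30% | 10% |

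The gap equals q with no true difference between arms. The cap plays no part, because it is two in both arms.

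**Challenges: number of surveys.** CAB-LA has 6 (months 1, 3, 5, 7, 9, 11) and oral has 12 (months 1 to 12), a ratio of 12/6 = 2. If each survey has the same probability p of a given challenge being reported, and answers are independent, the chance of ever reporting it is 1 − (1 − p)^k:

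- p = 0.05: 1 − 0.95^6 = 0.265; 1 − 0.95^12 = 0.460; gap 19.5 points.
- p = 0.10: 1 − 0.90^6 = 0.469; 1 − 0.90^12 = 0.718; gap 24.9 points.
- p = 0.20: 1 − 0.80^6 = 0.738; 1 − 0.80^12 = 0.931; gap 19.3 points.

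Independence is the most favourable assumption for a large gap, because a transport or stigma problem tends to persist. A beta-binomial model with within-person correlation ρ uses M = (1 − ρ)/ρ, a = pM, b = (1 − p)M, and P(ever) = 1 − ∏ (b + i)/(a + b + i) for i = 0 to k − 1. Each cell gives CAB-LA versus oral, then the gap in points:

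| p | ρ = 0.3 | ρ = 0.5 |
|---|---|---|
| 0.05 | 15.7% v 21.1%, 5 | 11.7% v 14.5%, 3 |
| 0.10 | 29.4% v 38.2%, 9 | 22.3% v 27.3%, 5 |
| 0.20 | 51.4% v 63.0%, 12 | 40.8% v 48.1%, 7 |

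With fully persistent answers the gap is 0. Restricted to the six shared months, k = 6 in both arms and the frequency gap is 0 under any of these models.

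**Challenges: the cap.** The oral list has 7 options besides the no-challenges one. Let each apply independently with probability p, and let a participant with more than two pick two at random. The recorded rate is p × E[min(1, 2/(1 + J))], with J binomial(6, p). True rates of 0.10, 0.20 and 0.30 are then recorded at about 0.10, 0.17 and 0.23. Without a cap they are recorded as they are.

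**The case against.** The strongest reply is that the effect is small and mostly manageable. The Study Outcomes Table types this endpoint as qualitative, and Section 7 gives it no test. If the plan's adherence proportions of .90 and .65 are borrowed as persistence (an assumption), about 70 × 0.10 = 7 CAB-LA and 35 × 0.35 ≈ 12 oral participants would give a stopping reason, so the comparison is descriptive whatever the wording. The CAB-LA write-in can be recoded for privacy, and concealment is asked about in both arms elsewhere, though not as a reason for stopping. The 6 and 12 survey schedules are stated openly. Section 4.1 mentions tailored items, but for acceptance, satisfaction and stigma perceptions; it gives no reason for different stopping options.

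Most of this stands and limits the weight of the point. It does not remove it: recoding the write-in cannot undo the joined oral option.

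Four stronger readings are tempting and not supported:

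- That the unequal cap distorts the comparison of why people stop. The stopping item allows two choices in both arms; only the challenges item differs.
- That unequal asking creates a 19 to 25 point gap in stopping reasons. Stopping is largely a one-time event, so repeated independent chances do not describe it. The figure concerns an ever-reported count of challenges, which Section 7 does not plan.
- That the CAB-LA form counts everyone who had side effects. Both side-effect options sit under a stem asking people who stopped for their reasons. Whether the two wordings shift counts, and in which direction, is uncertain.
- That nothing can be repaired after collection. This is true of the joined wording and the cap; the frequency effect can be removed by an analysis rule.

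**Conclusion.** The concern holds at modest weight. A stated secondary comparison rests on two forms that differ in three of eight stopping options without a route-related reason. The stigma option is the clear defect; the side-effect and difficulty wordings are lesser ones of uncertain effect. The stigma distortion equals the share of stoppers whose only such reason is privacy, which the documents do not give.

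For challenges, the unequal cap and the unequal number of surveys both break comparability. An ever-reported summary would be raised in oral by frequency alone by 19 to 25 points at most over the assumed 5 to 20% rates, falling to 3 to 7 points at correlation 0.5 and to 0 with fully persistent answers. The cap works the other way, and matters mainly when challenges are common.

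The primary persistence comparison does not use these items and is not affected.

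**What to change.** 1. Use identical wording on both forms for every stopping and challenge option that does not depend on route. Make privacy and judgement two separate options, and use one side-effect wording and one difficulty wording. Keep the daily-dose option in the oral form.
2. Apply the same selection rule to the challenges item in both arms.
3. Add to Section 7 that each participant's first reported stopping reason is counted once, using all survey months. A report with two choices would contribute both, once.
4. Add that challenges are compared between arms on months 1, 3, 5, 7, 9 and 11 only, with even-month oral answers reported descriptively.

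The cost is text edits to two app forms and a short addition to Section 7, with no extra visits or participants. The downside is that even-month oral challenge answers leave the between-arm comparison. Stopping reasons lose nothing, since all months are kept; the longer interval between CAB-LA surveys remains and should be noted when results are read.

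The branching in the oral form should be checked in the same edit. Its first question sends people still on PrEP to the item on why PrEP is no longer needed, not to the challenges item.

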Appendix D: Clinician Instruments

PROVIDER SURVEY (Note: baseline survey)

Thank you for agreeing to be part of this quality improvement project to improve care for those individuals taking PrEP. Your responses will remain confidential and anonymous.

Part 1. Information About You and Your Patients

1. What year were you born? [Write in]
2. How do you describe your gender (response optional)? [Select 1]
 - Female
 - Male
 - Transgender woman
 - Transgender man
 - Non-binary
 - Prefer not to answer
 - A gender not listed: [Write in]
3. Which of the following best describes your racial/ethnic background (response optional)? (Select all that apply)
 - African American/Black
 - Asian/Pacific Islander
 - Caucasian/White

- Hispanic/Latinx
- Native American/Alaska Native
- A race or ethnicity not listed: [Write in]

4. What is your role within the interprofessional team? [Select 1]

- Physician
- Physician assistant
- Nurse practitioner
- Nurse
- Medical assistant
- Pharmacist
- Case manager
- Social worker
- Clinic administrative staff
- A role on the interprofessional team not listed: [Write in]

5. What is your role in the clinic for providing long-acting cabotegravir to your patients? (Select all that apply)

- Prescribing
- Medication procurement and/or dispensing
- Administering injections
- Patient scheduling
- Coordinating clinic flow (i.e., room availability, nurse scheduling, availability of injection during appointment, etc)
- Providing wraparound services (i.e., transportation, housing support, mental health resources, etc.)
- Patient counseling
- A role not listed: [write in]

Part 2. Acceptability, Appropriateness, and Feasibility of Implementing Long-Acting Cabotegravir Injections

Acceptability of Intervention Measure (AIM)

	Completely disagree	Disagree	Neither agree nor disagree	Agree	Completely agree
1. Our clinic process for providing long-acting cabotegravir injections to our clients meets my approval.					

2. Our clinic process for providing long-acting cabotegravir injections to our clients is appealing to me.					
3. I like our clinic process for providing long-acting cabotegravir injections to our clients.					
4. I welcome our clinic process for providing long-acting cabotegravir injections to our clients.					

Intervention Appropriateness Measure (IAM)

	Completely disagree	Disagree	Neither agree nor disagree	Agree	Completely agree
1. Our clinic process for providing long-acting cabotegravir injections to our clients seems fitting.					
2. Our clinic process for providing long-acting cabotegravir injections to our clients seems suitable.					
3. Our clinic process for providing long-acting cabotegravir injections to our clients seems applicable.					
4. Our clinic process for providing long-acting cabotegravir injections to our clients seems like a good match.					

Feasibility of Intervention Measure (FIM)

	Completely disagree	Disagree	Neither agree nor disagree	Agree	Completely agree
1. Long-term use of cabotegravir injections in our clinic seem implementable.					
2. Long-term use of cabotegravir injections in our clinic seem possible.					

3. Long-term use of cabotegravir injections in our clinic seem doable.	○	○	○	○	○
4. Long-term use of cabotegravir injections in our clinic seem easy to continue.	○	○	○	○	○

Part 3. Barriers and Facilitators for Implementation of Long-Acting Cabotegravir for PrEP

- Please rate your confidence in **initiating** and **monitoring** long-acting cabotegravir for PrEP.
 - Very high
 - High
 - Moderate
 - Low
 - Very low
 - Not applicable
- Please rate your confidence in **administering** long-acting cabotegravir for PrEP.
 - Very high
 - High
 - Moderate
 - Low
 - Very low
 - Not applicable
- Please rate your confidence in **counseling** patients in HIV prevention, addressing barriers to using PrEP, and supporting persistence.
 - Very high
 - High
 - Moderate
 - Low
 - Very low
 - Not applicable

Please indicate how much you agree with the following:

	Strongly agree	Agree	Neutral	Disagree	Strongly disagree
4. People experience negative judgment because they take PrEP.	()	()	()	()	()
5. Someone taking PrEP would be seen by others as slutty.	()	()	()	()	()

6. People taking PrEP receive praise for being responsible.	()	()	()	()	()
7. Someone taking PrEP would be treated unfairly by their doctors.	()	()	()	()	()

8. What barriers do you foresee in the implementation of long-acting cabotegravir for PrEP?

[Select up to 2]

- Patient's ability to keep bimonthly appointments
- Patient's transportation for bimonthly appointments
- Flagging/Clinic awareness of missed visits
- Staffing resourcing for clinic flow
- Rescheduling missed injections
- Patients acquiring HIV due to missed dose/visit
- Management of patients with other needs
- Patient injection/soreness

9. Which structural changes or resources may help facilitate long-acting cabotegravir implementation in your clinic? [Select up to 2]

- Increased coordination with other departments (i.e., pharmacy)
- Purchasing new refrigerators
- Finding room space or working around room availability
- Adjusting or extending staff working hours
- Use of different staff for injections
- Making transportation arrangements for patient participants
- Expanding hours for injection visits (i.e., visits in morning or during lunch breaks)
- Accommodating patients needing to reschedule injection visits (i.e. using walk-in visits, same-day appointments)
- Other: [write in]

10. How helpful do you think your clients will find the TheraPay mobile health app in supporting persistence with PrEP?

- Very helpful
- Somewhat helpful
- Neither helpful or unhelpful
- Somewhat unhelpful
- Very unhelpful

11. Do you have a preference for prescribing long-acting cabotegravir or daily oral PrEP?

- Prefer long-acting cabotegravir
- Prefer oral daily PrEP
- No preference

12. How likely is it that your clinic will continue to offer cabotegravir following the completion of this study?

- Very likely
- Somewhat likely
- Neutral
- Somewhat unlikely
- Very unlikely

Thank you for taking the time to complete this survey. Please provide your work email address. Your email will not be tied to your survey responses and will only be used for the purposes of this quality improvement initiative.

- Work email address: [Write in]

THANK YOU FOR COMPLETING THIS SURVEY.

PROVIDER SURVEY (Note: 6 months, 12 months and end of study)

Thank you for agreeing to be part of this quality improvement project to improve care for those individuals taking PrEP. Your responses will remain confidential and anonymous.

Part 1. Information About You and Your Patients

6. What year were you born? [Write in]

7. How do you describe your gender? [Select 1]

- Female
- Male
- Transgender woman
- Transgender man
- Non-binary
- Prefer not to answer
- A gender not listed: [Write in]

8. Which of the following best describes your racial/ethnic background? (Select all that apply)

- African American/Black
- Asian/Pacific Islander
- Caucasian/White

- Hispanic/Latinx
- Native American/Alaska Native
- A race or ethnicity not listed: [Write in]

9. What is your role within the interprofessional team? [Select 1]

- Physician
- Physician assistant
- Nurse practitioner
- Nurse
- Medical assistant
- Pharmacist
- Case manager
- Social worker
- Clinic administrative staff
- A role on the interprofessional team not listed: [Write in]

10. What is your role in the clinic for providing long-acting cabotegravir to your patients? (Select all that apply)

- Prescribing
- Medication procurement and/or dispensing
- Administering injections
- Patient scheduling
- Coordinating clinic flow (i.e., room availability, nurse scheduling, availability of injection during appointment, etc)
- Providing wraparound services (i.e., transportation, housing support, mental health resources, etc.)
- Patient counseling
- A role not listed: [write in]

Part 2. Acceptability, Appropriateness, and Feasibility of Implementing Long-Acting Cabotegravir Injections

Acceptability of Intervention Measure (AIM)

	Completely disagree	Disagree	Neither agree nor disagree	Agree	Completely agree
1. Our clinic process for providing long-acting cabotegravir injections to our clients meets my approval.					

2. Our clinic process for providing long-acting cabotegravir injections to our clients is appealing to me.					
3. I like our clinic process for providing long-acting cabotegravir injections to our clients.					
4. I welcome our clinic process for providing long-acting cabotegravir injections to our clients.					

Intervention Appropriateness Measure (IAM)

	Completely disagree	Disagree	Neither agree nor disagree	Agree	Completely agree
1. Our clinic process for providing long-acting cabotegravir injections to our clients seems fitting.					
2. Our clinic process for providing long-acting cabotegravir injections to our clients seems suitable.					
3. Our clinic process for providing long-acting cabotegravir injections to our clients seems applicable.					
4. Our clinic process for providing long-acting cabotegravir injections to our clients seems like a good match.					

Feasibility of Intervention Measure (FIM)

	Completely disagree	Disagree	Neither agree nor disagree	Agree	Completely agree
1. Long-term use of cabotegravir injections in our clinic seem implementable.					
2. Long-term use of cabotegravir injections in our clinic seem possible.					
3. Long-term use of cabotegravir injections in our clinic seem doable.					
4. Long-term use of cabotegravir injections in our clinic seem easy to continue.					

Part 3. Barriers and Facilitators for Implementation of Long-Acting Cabotegravir for PrEP

13. Please rate your confidence in **initiating** and **monitoring** long-acting cabotegravir for PrEP.
- Very high
 - High
 - Moderate
 - Low
 - Very low
 - Not applicable
14. Please rate your confidence in **administering** long-acting cabotegravir for PrEP.
- Very high
 - High
 - Moderate
 - Low
 - Very low
 - Not applicable
15. Please rate your confidence in **counseling** patients in HIV prevention, addressing barriers to using PrEP, and supporting persistence.
- Very high
 - High
 - Moderate
 - Low
 - Very low
 - Not applicable
16. Please rate the impact of providing long-acting cabotegravir injections for PrEP on your **workload** in clinic.
- Large increase in workload
 - Moderate increase in workload
 - No change in workload
 - Moderate decrease in workload
 - Large decrease in workload
17. What barriers have you observed with the implementation of long-acting cabotegravir for PrEP?
[Select up to 2]
- Patient's ability to keep bimonthly appointments
 - Patient's transportation for bimonthly appointments
 - Flagging/Clinic awareness of missed visits
 - Staffing resourcing for clinic flow
 - Rescheduling missed injections

- Patients acquiring HIV due to missed dose/visit
 - Management of patients with other needs
 - Patient injection/soreness
18. Which structural changes or resources have been most helpful in facilitating long-acting cabotegravir implementation in your clinic? [Select up to 2]
- Increased coordination with other departments (i.e., pharmacy)
 - Purchasing new refrigerators
 - Finding room space or working around room availability
 - Adjusting or extending staff working hours
 - Use of different staff for injections
 - Making transportation arrangements for patient participants
 - Expanding hours for injection visits (i.e., visits in morning or during lunch breaks)
 - Accommodating patients needing to reschedule injection visits (i.e. using walk-in visits, same-day appointments)
 - Other: [write in]
19. How could the process for use of long-acting cabotegravir injections for PrEP be improved? [Select up to 2]
- Increased clinic staff
 - Redistribution of clinic duties to allow dedicated healthcare providers more time to support long-acting cabotegravir processes
 - Regular evaluation of LA-CAB processes for efficacy and potential problems
 - Additional staff education/training
 - Improve documentation/EMR
 - Improve communication and care coordination within the clinical team
 - Improve communication with clients using PrEP (i.e. reminders of upcoming appointments, rescheduling of missed appointments)
 - Other: [fill in blank]
20. For participants who stopped taking long-acting injectable PrEP, which of the following best describes the most common reason(s) why? [Select up to 2]
- They no longer have an indication or need for PrEP
 - They found it too difficult to take PrEP as prescribed with their lifestyle
 - They felt stigmatized by others for taking PrEP
 - They experienced side effects from taking PrEP
 - They take too many medications
 - They felt there were too many appointments as part of PrEP care
 - They tested positive for HIV

21. How helpful do you think your clients find the TheraPay mobile health app in supporting persistence with PrEP?

- Very helpful
- Somewhat helpful
- Neither helpful or unhelpful
- Somewhat unhelpful
- Very unhelpful

22. Do you have a preference for prescribing long-acting cabotegravir or daily oral PrEP?

- Prefer long-acting cabotegravir
- Prefer oral daily PrEP
- No preference

23. How likely is it that your clinic will continue to offer cabotegravir following the completion of this study?

- Very likely
- Somewhat likely
- Neutral
- Somewhat unlikely
- Very unlikely

Thank you for taking the time to complete this survey. Please provide your work email address. Your email will not be tied to your survey responses and will only be used for the purposes of this quality improvement initiative.

- Work email address: [Write in]

THANK YOU FOR COMPLETING THIS SURVEY.

